**1.0 Purpose of the study:**

**Aim 1 will characterize PD-MCI (Parkinson's disease mild cognitive impairment), PDN (Parkinson's disease without cognitive impairment), and HA (healthy adult) spoken discourse, cognitive, and motor speech profiles.** Phase 2 biomarker development requires robustly characterized cohorts in which to test candidate biomarkers. Using a standardized battery of cognitive, language, and motor speech tests PD participants will be assigned to PD-MCI (single/multi-domain) or PDN groups. We propose collecting spoken discourse samples using standardized elicitation protocols. The same tasks will be extracted from the extant HA database. Researchers will transcribe, code, and analyze discourse samples. Group differences (including sub-analyses for single and multi-domain MCI subtypes), elicitation stimuli effects, and group x stimuli interactions will be examined using multivariate and mixed-design ANOVA procedures.

**Aim 2 will develop and evaluate the classification accuracy of an optimally weighted discourse classification function for PD-MCI and PDN.** We propose using discriminant function analysis to identify an optimized composite variable that best predicts PD-MCI, PDN, and HA group membership. Sensitivity/specificity analyses, positive/negative predictive values, and receiver operating characteristic curves will be used to evaluate the discourse classification function properties.

The **primary endpoint** is an optimally weighted discourse function that can classify PD-MCI with > 80% sensitivity/specificity.

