**2.0 Background / Literature Review / Rationale for the study:**

Individuals with Parkinson's disease (PD) have a 6-fold increased risk of dementia. PD mild cognitive impairment (PD-MCI) is thought to be a transitional state to dementia for

many of those affected. **Difficulties monitoring early cognitive impairments, and concomitant delays in treatment initiation, are major barriers** to the accurate diagnosis of and the development of interventions for cognitive impairments in PD. A biomarker is any characteristic that can be objectively measured and indicates normal/pathogenic processes or responses to therapeutic interventions. Biomarkers can be genetic markers, neural markers, and observable behaviors. In the absence of neuropsychological findings, early dementia can still be detected in spoken discourse. Thus, a **spoken discourse biomarker** can be a valuable supplement to extant neuropsychological evaluation for **monitoring cognitive-linguistic changes in real world environments**. The **long-term objective** of this research is to improve the early and accurate diagnosis of PD cognitive impairment with a reliable spoken discourse biomarker. Research shows that discourse features including grammar errors, information content/efficiency, coherence, and verbal disfluencies hold promise for detecting PD cognitive impairments. Additionally, our pilot suggests that an optimally weighted composite variable, and no one single variable, is best able to discriminate PD spoken discourse. A **major barrier** is the absence of a spoken discourse biomarker that has been rigorously developed and tested on a meticulously-characterized cohort of PD-MCI, PD without cognitive impairment (PDN), and healthy adults (HA). Using the Fit-for-Purpose framework, **the goal of the proposed research is to complete a Phase 2 spoken discourse biomarker study**. The **overarching hypothesis** is that PD-MCI and PDN will have unique profiles of spoken discourse impairments that are distinguishable from each other and from HA.

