### 3.0 Inclusion and Exclusion Criteria:

Only individuals with PD will be newly recruited and enrolled as part of the study. Healthy adult data will be extracted from extant databases (publicly available) from NIH-funded studies.

Inclusion Criteria Person with Parkinson's disease without cognitive impairment

- Age 50-90 years
- Diagnosis of idiopathic Parkinson's disease (UK Brain Bank criteria) made by a movement disorders specialist
- Under the care of a movement disorders specialist for a minimum of 1-year duration
- Native monolingual English speaker
- Hoehn & Yahr score between 1.5 and 4
- Grade 10 education, or higher
- Sufficient vision and hearing (aided or unaided) for all experiment tasks
- Montreal Cognitive Assessment (or MoCA-converted MMSE score) greater than or equal to 25
- No subjective complaints of cognitive difficulty or word finding issues

Inclusion Criteria Person with Parkinson's disease mild cognitive impairment

- Age 50-90 years
- Diagnosis of idiopathic Parkinson's disease (UK Brain Bank criteria) made by a movement disorders specialist

- Under the care of a movement disorders specialist for a minimum of 1-year duration
- Native monolingual English speaker
- Hoehn & Yahr score between 1.5 and 4
- Grade 10 education, or higher
- Sufficient vision and hearing (aided or unaided) for all experiment tasks
- Montreal Cognitive Assessment (or MoCA-converted MMSE score) greater than or equal to 17
- Subjective complaints of cognitive difficulty or word finding issues, without significant impact on activities of daily living

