Communication Participation Item Bank measure – pen and paper tool measuring communication quality of life

reminder call, staff members will complete the Participant/Visitor health screener for (attached to protocol). If participants answer ‘yes’ to any item, staff members will request that their study visit be rescheduled at a time that is convenient for the participant. If the participant answers ‘yes’ to any of the questions under the ‘Travel’ heading then they will be provided with the COVID-19 contact information handout (attached). This information will be emailed to the participant if required. Information will also be provided over the telephone including the email and telephone contacts for the Illinois Department of Public Health.

If the participant cannot be contacted by telephone, the screening form can be completed in person at the time of the study visit (but prior to initiating any substantial participant contact). Visitors who accompany the participant will also be asked to complete a health screener, if they intend to wait in the research lab lobby space. Health screening tools will be stored in a locked filing cabinet in the PIs lab for a period of 60 days following the participant’s visit. Following this period, forms will be shredded using secure shredding boxes located in the NUCASLL clinic/Pis home department (CSD).

During the **screening portion** of the visit, participants will complete the Montreal Cognitive Assessment (MoCA), an audiometric hearing assessment, and a vision screening using a Snellen eye chart. Participants meeting the inclusion criteria for the study will advance immediately to the experiment tasks. Those not meeting the inclusion criteria will be provided summary results, including the criteria that they did not meet (i.e., cognition, hearing, vision) and will be advised to discuss these results with their healthcare team.

During the **experiment portion** of the visit participants will complete the following tasks:

Descriptive and Neuropsychological Testing Measures – The measures in the table below are standard descriptive measures for the population and the research aims under study. These are all standard clinical measures in PD clinical practice. Standardized language and cognitive neuropsychological measures will be used to stratify participants into PD-MCI and PD normal cognition groups using the Movement Disorders Society Task Force published guidelines.

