Sentence Intelligibility Test (SIT-5). Set of 11-sentences generated for each participant. Sentences are phonetically balanced and are read aloud by the participant. Measure of speech intelligibility
Standardized oral reading passage (speech rate and intelligibility)
Brief motor speech exam
Demographic form (attached)
National Adult Reading Test
Neuropsychological Measures Used in Primary Analyses and to Classify Participants into MCI-PD from PDN (no cognitive impairment) groups
Trail Making Test-A (In-person testing)
Trail Making Test-B (In person testing)
10-points Clock Drawing Test + Clock copying
Free and Cued Selective Reminding Test from the Arizona Battery of Communication Disorders of Dementia (In-person testing)
Brief Visuospatial Memory Test-Revised
Semantic Fluency-animals
Digit span forward and backward
Stroop Color-word Interference
Boston Naming Test (30-item version)
Verb Naming Subtest – Northwestern Assessment of Verbs and Sentences
Sentence Production Priming subtest of the Northwestern Assessment of Verbs and Sentences
Pyramids and Palm Trees Test - object semantics
CERAD 10-Word List (Remote testing)

Discourse Sampling (main study outcome measure)

Using standardized spoken discourse elicitation stimuli and instructions, participants will be asked to generate a story about a series of events occurring in: 1) a series of six black and white line drawings and 2) a wordless picture book. Participants will generate a maximum of four spoken discourse samples. Each discourse sample is estimated at 2 to 4 minutes in length. Audio files will be transcribed using a HIPAA compliant transcription service/software. Once transcribed, files will be coded in [name] lab for a number of discourse (e.g., story structure, information content), speech (e.g., pauses, number of words), and language variables (e.g., grammar/syntax).

Proposed Data Analysis

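### PD-MCI is partly defined by language tests that overlap with the discourse function, so a pooled sensitivity above 80% would not show how well non-language PD-MCI is detected

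*Combined protocol and SAP*

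**What the plan says.** **Endpoint.** Section 1.0 sets the primary endpoint as "an optimally weighted discourse function that can classify PD-MCI with > 80% sensitivity/specificity". It is not limited to any cognitive domain.

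**How the groups are formed.** Section 8.0, Data Sources, says "Standardized language and cognitive neuropsychological measures will be used to stratify participants into PD-MCI and PD normal cognition groups", following published task-force guidelines. The table of tests is headed "Neuropsychological Measures Used in Primary Analyses and to Classify Participants into MCI-PD from PDN (no cognitive impairment) groups". Its 13 rows include semantic fluency, object naming, the "Verb Naming Subtest – Northwestern Assessment of Verbs and Sentences" and the "Sentence Production Priming subtest of the Northwestern Assessment of Verbs and Sentences". They also include a semantic-association test and non-language tests (trail making, clock drawing, memory, digit span, Stroop).

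**Entry complaint.** Under Section 3.0 the PD-MCI group must report either cognitive difficulty or word-finding trouble. The PDN criterion is "No subjective complaints of cognitive difficulty or word finding issues".

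**What the function measures.** Section 2.0 states that "discourse features including grammar errors, information content/efficiency, coherence, and verbal disfluencies hold promise for detecting PD cognitive impairments". Section 8.0 adds story structure, pauses, word counts and grammar or syntax to what is coded. Aim 2 selects among the discourse measures by stepwise discriminant analysis.

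**Subtypes.** The only subtype analysis is the single- versus multi-domain split in Aim 1 (Section 1.0). Aim 2 in Section 8.0 describes sensitivity, specificity and ROC curves without any breakdown by impaired domain.

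**The concern.** Someone classed as PD-MCI after failing naming or sentence production has failed on abilities close to those that grammar and disfluency scores reflect. Someone classed as PD-MCI through memory, attention or visuospatial tests has not. It is plausible, though not shown in the documents, that the function detects the first kind more readily. A single pooled sensitivity averages the two.

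The stated purpose makes this matter. Section 2.0 presents the marker as a supplement to neuropsychological evaluation and argues that discourse can reveal early dementia even when neuropsychological testing is clear. If high sensitivity came mainly from cases that the language tests had already flagged, the function would add little to those tests, and the figure would not carry over to other PD-MCI. The endpoint could be met either way, and the planned output would not tell a reader which had happened.

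**Working it through.** **1. The plan's own figure.** Section 4.0 gives 129 participants for sensitivity 0.83, precision 0.10, 90% confidence and 30% prevalence. Cases needed = 1.645² × 0.83 × 0.17 / 0.10² = 38.2. Total = 38.2 / 0.30 = 127.3, so 128, or 39 / 0.30 = 130 if cases are rounded up first. The stated 129 is reproduced to within rounding. With the planned 43 PD-MCI cases the half-width at 0.83 is 0.094. The sample size is not in question here.

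**2. What the endpoint requires.** 0.80 × 43 = 34.4, so at least 35 of 43 must be detected (81.4%).

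**3. What a pooled 80% allows.** Let w be the share of PD-MCI cases with a language-domain failure, Se_L the sensitivity in them and Se_N the sensitivity in the rest. Then pooled Se = w·Se_L + (1 − w)·Se_N, so the Se_N needed for a pooled 0.80 is (0.80 − w·Se_L) / (1 − w). The documents give none of w, Se_L or Se_N; every value below is an assumption.

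| w | Se_L = 0.90 | Se_L = 0.95 | Se_L = 1.00 |
|---|---|---|---|
| 0.4 | 0.733 | 0.700 | 0.667 |
| 0.5 | 0.700 | 0.650 | 0.600 |
| 0.6 | 0.650 | 0.575 | 0.500 |
| 0.7 | 0.567 | 0.450 | 0.333 |

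Example: (0.80 − 0.5 × 0.95) / 0.5 = 0.65, and (0.80 − 0.6 × 0.95) / 0.4 = 0.575.

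**4. In whole cases.** Each line totals 35/43:
- 22 language cases, 21 detected; 21 others, 14 detected (67%, exact 90% CI 46% to 83%).
- 26 language cases, 25 detected; 17 others, 10 detected (59%, exact 90% CI 36% to 79%).
- 30 language cases, 28 detected; 13 others, 7 detected (54%, exact 90% CI 29% to 78%).

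**5. Whether a planned analysis would show it.** The single- versus multi-domain split would not: a single-domain case may be language or memory, and a multi-domain case may or may not include language. It also belongs to Aim 1 group differences, not to classification accuracy. Nothing in Aim 2 stratifies by domain.

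**The case against.** The strongest reply is that this is not an error. Language is a legitimate PD-MCI domain, and any marker of a heterogeneous condition can have uneven subgroup sensitivity. Section 2.0 describes the intended use as monitoring change that is both cognitive and linguistic, so some overlap is deliberate. This stands as a reason to leave the group definition alone. It does not narrow the endpoint, which is stated for PD-MCI without qualification.

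Three stronger readings are tempting, and the documents do not support them.

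- A reader might infer that the reference standard incorporates the index test. It does not: the discourse samples are listed separately as the main outcome and do not assign groups. Coherence, story structure and pauses are also not direct counterparts of naming or sentence tests.
- A reader might infer that a word-finding complaint makes someone PD-MCI. It satisfies one entry item; the test battery still does the assigning.
- A reader might infer that language cases will carry the result. The plan does not give the share of such cases. The number of failures required, and which tests count toward which domain, rest on guidelines not reproduced in it. Four of the 13 rows require word or sentence production, but a row count is not a share of cases. At a 50% share, even perfect detection of language cases still requires 60% in the rest; a large gap needs a share well above half.

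**Conclusion.** The point holds as a limit on interpretation. The reference classification and complaint criterion share part of their construct, language production and word finding, with the discourse function. A pooled sensitivity above 80% could therefore coexist with clearly lower detection of PD-MCI without language impairment, and no planned analysis would show it. With an assumed 95% detection in language cases, detection in the rest could be as low as 65% (half the cases language-impaired) or 57.5% (60% language-impaired) with the pooled figure still at 80%. These values show what is possible, not what is likely. The real size cannot be estimated from the documents, and neither the sample size nor the group definition needs to change on this account.

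**What to change.** In Aim 2, prespecify sensitivity at the chosen cut-off separately for PD-MCI with and without a language-domain failure on the tests listed in Section 8.0, each with an exact confidence interval. State in advance which domain semantic fluency counts toward, because that choice moves cases between strata. Label the split descriptive. Beside the pooled result, state that it applies to the enrolled mix of PD-MCI, and that accuracy in non-language PD-MCI is only as well established as that stratum's estimate and interval show.

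Two further steps may suggest themselves and are not recommended. Making a general claim conditional on the non-language stratum being compatible with the pooled figure would not work: at 14/21 (67%) the exact 95% CI is 43% to 85%, which contains 81%, so the unfavourable case would pass. Re-forming the groups without the language tests would move language-impaired people who entered with a complaint into PDN, against Section 3.0, and a fall in accuracy could not then be interpreted.

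The cost is one table and one sentence of conclusion, on data already planned. The drawback is precision: at a sensitivity of 0.83 the approximate 90% half-width is 0.13 with 21 cases and 0.17 with 13, against 0.094 for all 43.

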**Aim 1**

Multivariate ANOVA statistical procedures will be used to examine group differences on neuropsychological test measures and spoken discourse measures. Follow-up univariate ANOVAs and Tukey's post-hoc tests will be used to further examine significant individual variables from the multivariate testing and to examine group contrasts (healthy controls, PD without cognitive impairment, and PD-MCI). If required based on group differences in descriptive variables age, sex, depression measure scores, and education will be entered as covariates.

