**Inclusion Healthy Adults (from extant data base – no new recruiting)**

- Age 50-90 years
- Montreal Cognitive Assessment (or MoCA-converted MMSE score) greater than or equal to 26
- Native monolingual English speaker
- Grade 10 education, or higher
- Sufficient vision and hearing (aided or unaided) for all experiment tasks

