## **4.0 Sample Size:**

We will enroll 86 PD participants (43 individuals with PD and normal cognition and 43 individuals with PD mild cognitive impairment). Data from 43 age/education/sex matched HA will be sampled from an extant repository.

Sample sizes for ANOVA and DFA were calculated using G\*Power. For Aim 1, a sample of 129 participants for MANOVA procedures with 3 IVs (PD-MCI, PDN, HA), 15 dependent variables (6 canonical variables), and up to 3 covariates will detect a minimum of  $f^2$  of 0.16 (medium-sized effects) with power of 0.90, and  $\alpha=0.05$ . The available effect size estimates for the 8 candidate discourse variables range from  $f^2$  of 0.33 to 0.50 (medium to large effects). With the smallest anticipated effect size based on our pilot data ( $f^2 = .33$ ) 129 participants in a mixed ANOVA with 2 IVs (Group [3 levels]) and Task [2 levels]) with up to 2 covariates will yield power of 0.86,  $\alpha=0.05$ . At the highest estimated effect size ( $f^2 = .50$ ), the same sample size will yield power of 0.99,  $\alpha=0.05$ . For **Aim 2**, DFA procedures with 3 groups and 8 discourse variables with 129

participants will detect  $f^2$  of .10 (small-medium effects) with power of 0.90,  $\alpha=0.05$  and power of 0.85, if  $\alpha=0.025$ . For the sensitivity and specificity analyses a sample of 129 participants will detect sensitivity and specificity values of 0.83 or higher with a 90% confidence interval precision of 0.10, given an expected disease (PD-MCI) prevalence of 30%, a conservative prevalence estimate. This precision level is consistent with guidelines for Phase 2 studies.

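### Aim 1 follow-up tests use Tukey with one pooled error variance; if PD-MCI is the more variable group, PDN versus HA loses power, and an unequal-variance method would prevent this cheaply

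*Combined protocol and SAP*

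**What the plan says.** Section 8.0, Proposed Data Analysis, Aim 1, plans a multivariate ANOVA on the neuropsychological and discourse measures. For variables that are significant there, "Follow-up univariate ANOVAs and Tukey's post-hoc tests will be used", among other things "to examine group contrasts (healthy controls, PD without cognitive impairment, and PD-MCI"). Age, sex, depression score and education may enter as covariates. The section names no variance check and no method for unequal variances.

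Section 4.0 sets equal groups: "We will enroll 86 PD participants (43 individuals with PD and normal cognition and 43 individuals with PD mild cognitive impairment"), and "Data from 43 age/education/sex matched HA will be sampled from an extant repository".

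Section 3.0 sets the cognitive entry rules:
- HA: "Montreal Cognitive Assessment (or MoCA-converted MMSE score) greater than or equal to 26"
- PDN: "Montreal Cognitive Assessment (or MoCA-converted MMSE score) greater than or equal to 25", with no cognitive complaint
- PD-MCI: "Montreal Cognitive Assessment (or MoCA-converted MMSE score) greater than or equal to 17", with a complaint and no upper limit

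The table of measures in section 8.0 heads the test battery "Neuropsychological Measures Used in Primary Analyses and to Classify Participants into MCI-PD from PDN", so the same tests assign the PD groups and serve as outcomes. Section 1.0 states that PD-MCI contains single- and multi-domain cases.

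**The concern.** Tukey's test divides every pairwise difference by a standard error built from the same pooled variance. If one group is more variable, that standard error is too large for the pair that excludes it and too small for the pairs that include it. Equal group sizes largely protect the omnibus F test, but not the individual contrasts.

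Three features of the plan make PD-MCI the likely wide group. Its permitted MoCA range is much longer. It mixes subtypes, so on any one test some members are impaired and others are not. And the PD groups are split on the outcome tests, which selects PDN for the absence of low scores and narrows its spread.

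The overarching hypothesis in section 2.0 is that PD-MCI and PDN differ from each other and from HA, so PDN versus HA is a required contrast. Under Tukey it can lose power to variance from a group outside the comparison, and a missed difference could then be read as evidence that PDN discourse or cognition is like that of HA.

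**Working it through.** **The plan's own figure.** No power or SD is stated for any pairwise contrast. The nearest figure is the 0.86 power for the Aim 1 mixed ANOVA in section 4.0. It could not be reproduced for the group effect, but that is a separate matter and nothing below depends on it.

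**Inputs.** From the documents: n = 43 per group, three pairwise contrasts, α = 0.05. Assumed: normal data, SDs of 1 (HA), 1 (PDN) and k (PD-MCI), and a PDN versus HA difference of 0.7 SD. The Tukey critical value as a t statistic (3 groups, 126 df) is 2.372.

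**Step 1: standard errors.** The pooled variance is (1 + 1 + k²)/3.
- PDN versus HA: the pooled SE divided by the true SE is √[(2 + k²)/3].
- Any PD-MCI contrast: the true SE divided by the pooled SE is √{[(1 + k²)/2] / [(2 + k²)/3]}.

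At k = 1.5 the first is √(4.25/3) = 1.19 and the second is √(1.625/1.417) = 1.07.

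| k | PDN vs HA, pooled/true SE | PD-MCI contrasts, true/pooled SE |
|---|---|---|
| 1.25 | 1.09 | 1.04 |
| 1.5 | 1.19 | 1.07 |
| 2 | 1.41 | 1.12 |

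**Step 2: power and error rates by simulation.** The runs (20,000 to 200,000 data sets each) agree to within about 0.01 for power and a few thousandths for error rates.

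| k | PDN vs HA power, Tukey | PDN vs HA power, Games-Howell | Error per PD-MCI contrast, Tukey | Familywise error, Tukey |
|---|---|---|---|---|
| 1 | 0.81 | 0.80 | 0.019 | 0.050 |
| 1.25 | 0.74 | 0.80 | 0.024 | 0.051 |
| 1.5 | 0.66 | 0.80 | 0.029 | 0.054 |
| 2 | 0.46 | 0.80 | 0.037 | 0.058 |

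Error rates are under the full null. With Games-Howell the error per PD-MCI contrast stays at 0.019 to 0.020. Across runs, the Tukey figures for k = 1.25 to 2 reach 0.038 per contrast and 0.060 familywise. At equal SDs the power comparison is 0.809 (Tukey) against 0.804 (Games-Howell).

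**Step 3: how large might k be?** The documents do not say. Two illustrations bracket it.
- *MoCA floors only.* Assume a MoCA maximum of 30 and scores uniform over the permitted range. The SDs are then about 1.4 (HA), 1.7 (PDN) and 4.0 (PD-MCI). For an outcome correlated r with MoCA within PD-MCI, and equal residual variance, k = 1/√[r²(1.7/4.0)² + 1 − r²]. This gives 1.04, 1.12 and 1.29 at r = 0.3, 0.5 and 0.7. Tukey power is then 0.80, 0.78 and 0.73, against 0.80 with Games-Howell. A ratio of 1.5 needs r of about 0.82.
- *Subtype mixing and selection on the tests.* Assume half of PD-MCI is impaired by 1.5 SD on a given test. The PD-MCI SD is √(1 + 0.25 × 1.5²) = 1.25. If PDN is also truncated at −1.5 SD, its SD is 0.88, so the PD-MCI to PDN ratio is 1.25/0.88 ≈ 1.4. This route does not depend on correlation with MoCA.

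**The case against.** A reader might infer that the entry rules themselves give the three groups very different spreads. The documents do not support that. They give no SD for any outcome in any group, and the MoCA floors are screening limits: MoCA is not among the tests listed for the primary analyses. HA and PDN start at 26 and 25, so one group is expected to differ, not three. Taken alone, the floors imply modest ratios for outcomes moderately correlated with MoCA. The case is weakest for the discourse measures, which are the main outcome. This stands. Subtype mixing and selection on the tests can widen the gap beyond the MoCA-only figures, but the documents do not quantify them.

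A reader might also infer that PD-MCI contrasts are seriously anti-conservative. They are not: each stays below 0.05, and familywise error stays close to 0.05. The plan also restricts follow-up tests to variables significant in the multivariate test. Adding just a univariate F gate brings familywise error under the full null to 0.046, 0.049 and 0.055 at k = 1.25, 1.5 and 2. The gate gives no such protection when only some groups differ, but the excess remains small.

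Finally, the primary endpoint is classification by discriminant analysis, which does not use these tests, and the 0.7 SD difference has no source in the documents. Both points hold, and they limit the weight of the concern.

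**Conclusion.** The concern holds in conditional form. The plan fixes a pooled-variance test where one group is plausibly more variable, and it names no alternative. The main harm is lost power for PDN versus HA: about 6 points at an SD ratio of 1.25 (0.80 to 0.74) and 34 points at a ratio of 2 (0.80 to 0.46). Liberality of the PD-MCI contrasts is a minor matter. These sizes rest on assumed SD ratios, normal data and an assumed 0.7 SD difference. The premise is strongest for the neuropsychological tests that also define the PD groups. This is a cheap improvement to Aim 1, not a demonstrated error, and it leaves the primary endpoint untouched.

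**What to change.** In section 8.0, Proposed Data Analysis, Aim 1:
- Replace Tukey with Games-Howell comparisons, following Welch ANOVA, for the unadjusted follow-up tests.
- Where covariates or the task factor are in the model, use group contrasts with group-specific residual variances or HC3 standard errors, with the same three-pair adjustment. Games-Howell does not cover these models. With the task factor each participant contributes repeated measures, so the repeated-measures structure must be kept as well.

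Fix the choice before the data are seen, not after a variance test.

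The cost is about half a point of power if variances are equal (0.809 against 0.804). The unadjusted change is one line and uses standard software, while the adjusted and mixed models need slightly more work. The change does not address the pooled covariance matrix in the preceding multivariate ANOVA.

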### Extant Data Collection (Healthy Adult data)

Demographic data and neuropsychology testing measures for the healthy control sample will be secured from an extant dataset in a secure repository ICPSR 3664 (Harris Wright, Heather, and Capilouto, Gilson J. Discourse Processing in Healthy Aging in the United States. Ann Arbor, MI: Inter-university Consortium for Political and Social Research [distributor], 2017-03-02. <https://doi.org/10.3886/ICPSR36634.v1>). Audio and video files of spoken discourse samples for the same study (study of normal aging and discourse) are curated with the Carolina Conversations Collection and are available for use in research with an approved IRB (<http://carolinaconversations.musc.edu/about/>).

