## **C. APPROACH**

Observational, cross-sectional study with three cohorts: healthy older adults, individuals with Parkinson's disease without cognitive impairment, and individuals with Parkinson's disease with mild cognitive impairment.

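### Aim 1 adjusts for age, sex and education only if the groups are judged to differ, with no criterion stated; this leaves some bias in PD-MCI versus PDN and gives up a little precision

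*Combined protocol and SAP*

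**What the plan says.** Section 8.0, Proposed Data Analysis, Aim 1, plans a MANOVA across the three groups, then univariate ANOVAs and Tukey contrasts. On adjustment it says: "If required based on group differences in descriptive variables age, sex, depression measure scores, and education will be entered as covariates". It does not say how a group difference is to be judged. No other section fixes a covariate.

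Section C (Approach) describes the design as "Observational, cross-sectional study with three cohorts". Section 4.0 sets the PD sample: "We will enroll 86 PD participants (43 individuals with PD and normal cognition and 43 individuals with PD mild cognitive impairment". For controls it says: "Data from 43 age/education/sex matched HA will be sampled from an extant repository". No matching of PD-MCI to PDN is described.

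Section 4.0 allows for covariates in two places, with different counts. The MANOVA is sized as "a sample of 129 participants for MANOVA procedures with 3 IVs (PD-MCI, PDN, HA), 15 dependent variables (6 canonical variables), and up to 3 covariates". The mixed ANOVA, "with up to 2 covariates will yield power of 0.86". The Aim 1 sentence names four candidates.

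**The concern.** This is a look-then-adjust rule. At 43 per group a difference test seldom detects a small-to-moderate gap in age or education, yet such a gap still shifts the outcome contrast if the covariate predicts discourse performance. A covariate left out because its difference was not significant may still be confounding. Age, education and sex are also the variables chosen for matching HA, so the plan already treats them as relevant, and matching variables normally stay in the model.

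At stake are the Aim 1 contrasts, chiefly PD-MCI versus PDN, which has no protection by design. Part of a reported discourse difference could be an age or education difference. Because no criterion is named, the choice of model is also left to judgement after the data are seen.

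**Working it through.** **Inputs from the documents.** 43 per group, 129 in total; alpha 0.05; three non-randomised cohorts; HA matched on age, education and sex.

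**Assumptions, because the documents give no figure.** The trigger is a two-sided 5% test; the true PD-MCI/PDN gap is 0.2 to 0.5 covariate SD; the covariate-outcome correlation r is 0.2 to 0.5; the slope is linear and common to the groups.

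**1. The plan's own figures.** For the MANOVA (f² = 0.16, stated power 0.90), use Pillai's trace with df1 = 15 × 2 = 30 and df2 = 2 × (129 − 6 − 15 + 2) = 220. Taking λ = f² × df2 = 0.16 × 220 = 35.2 gives power 0.919, within 2 points of the plan. Taking λ = f² × N × 2 = 0.16 × 129 × 2 = 41.28 gives 0.963. The mixed-ANOVA figure of 0.86 is matched (0.853) if 0.33 is read as f with numerator df 4; with numerator df 2 it is 0.923. This point disputes neither figure.

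**2. What a 5% test can flag.** The smallest observed gap that reaches significance is t(0.975, 84) × √(2/43) = 1.989 × 0.2157 = 0.43 SD.

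| True gap (SD) | Flagged, 43 v 43 t-test | Not adjusted | Flagged, three-group F (depends on pattern) |
|---|---|---|---|
| 0.2 | 15% | 85% | not computed |
| 0.3 | 28% | 72% | 22–28% |
| 0.4 | 45% | 55% | 36–46% |
| 0.5 | 63% | 37% | 52–66% |

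For sex, 65% v 50% is flagged 29% of the time and 70% v 50% is flagged 47%. With a 10% threshold, a 0.4 SD gap is flagged 58% of the time.

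**3. Bias left by the rule.** With no true group effect, never adjusting gives bias r × gap, for example 0.3 × 0.4 = 0.12 SD. Under the rule, mean bias is about (share not flagged) × (bias when not flagged). Two-group simulation, 20,000 runs per setting:

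| Gap | r | Bias when not flagged | Mean bias, rule | Type I error, rule | Type I error, always adjust |
|---|---|---|---|---|---|
| 0.3 | 0.3 | 0.061 | 0.044 | 0.052 | 0.050 |
| 0.3 | 0.5 | 0.100 | 0.073 | 0.055 | 0.049 |
| 0.4 | 0.3 | 0.075 | 0.041 | 0.054 | 0.050 |
| 0.4 | 0.5 | 0.123 | 0.066 | 0.058 | 0.048 |
| 0.5 | 0.3 | 0.085 | 0.032 | 0.053 | 0.048 |
| 0.5 | 0.5 | 0.141 | 0.052 | 0.062 | 0.055 |

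Check on the first row: (1 − 0.278) × 0.061 = 0.044. Always adjusting leaves a mean bias of about 0 in every row.

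A three-group version puts HA midway and triggers on the three-group ANOVA at 5%. It flags gaps of 0.25, 0.375 and 0.5 SD in about 16%, 32% and 52% of studies. For r = 0.2 to 0.5 the mean bias is 0.03 to 0.10 SD.

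**4. Precision.** For a balanced covariate the standard error shrinks by the factor √(1 − r²). At r = 0.3 this is √0.91 = 0.954, or 4.6% smaller; at r = 0.5 it is √0.75 = 0.866, or 13.4% smaller. Where the groups differ on the covariate the gain is less: at a 0.4 SD gap the simulated standard error falls from 0.215 to 0.210 (r = 0.3) or 0.191 (r = 0.5). Three-group power at f = 0.25 rises from 0.710 to 0.753 (r = 0.3) or 0.835 (r = 0.5).

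**5. Cost of always adjusting.** Error degrees of freedom go from 129 − 3 = 126 to 123. If the covariates are unrelated to outcome, power at f = 0.33 (numerator df 2) is 0.923 with 0, 2 or 3 of them.

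**The case against.** The strongest reply is that the plan names no significance test, so the flagging rates describe an assumed procedure. That is right, and a looser threshold would flag more. But an unnamed criterion is part of the problem, because the covariate set is then settled after the data are seen. The gap and the correlation are also assumed. The near-zero bias under constant adjustment holds for a measured covariate with a linear, common slope, and observational cohorts may differ in other ways too.

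Four stronger readings are tempting, and the material does not support them.

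- *The p-values are invalid.* A reader might infer this from a data-dependent model. For a single contrast tested at 0.05, the three-group simulation reaches about 0.07 only at the strongest correlation. The plan uses Tukey contrasts, and under that criterion the error for this contrast is 0.019 to 0.030, against 0.017 to 0.023 when always adjusting.
- *Imbalance of any moderate size usually goes unadjusted.* This fails at 0.5 SD, where 52% to 63% of studies are flagged in the main calculations.
- *A depression covariate would remove all 43 HA.* The depression scale is listed with the measures taken on PD participants, and of the HA source section 5.0 says: "Demographic data and neuropsychology testing measures for the healthy control sample will be secured from an extant dataset". That clause does not list instruments, so whether a depression score exists there is unknown.
- *HA matching must fail because one HA set cannot match two PD groups.* This presumes a PD-MCI/PDN difference that the documents do not report. Matching does limit imbalance in the HA contrasts.

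The covariate counts are ceilings set against a list of candidates, so they conflict only if more covariates trigger than were allowed for. The effect on power is negligible, but the text should agree.

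**Conclusion.** The point holds in a limited form. Adjustment for age, sex and education in Aim 1 depends on an unstated reading of observed differences, in a comparison with neither randomisation nor described matching. If the trigger is a 5% test, true gaps of about 0.2 to 0.4 SD are missed more often than not. For r between 0.2 and 0.5 the average cost is about 0.03 to 0.10 outcome SD of bias in PD-MCI versus PDN. There is also a modest loss of precision, which matters mainly if r is near 0.5. The trigger, the gap and the correlation are all assumptions. Residual bias and lost precision are the reasons to change the rule; type I error is a minor matter. The primary endpoint, the classification accuracy of the Aim 2 discriminant function, does not use this rule. The change is worth making because it is cheap, but the rule is not a fatal flaw.

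**What to change.** Replace the covariate sentence under Aim 1 with:

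*Age, sex and education are covariates in every Aim 1 MANOVA, follow-up ANOVA and mixed ANOVA, regardless of observed group differences; contrasts are reported as adjusted means.*

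Add that depression score is a sensitivity covariate in PD-MCI versus PDN only, unless the HA repository is confirmed to hold the same scale.

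In section 4.0, change the mixed-ANOVA allowance from two covariates to three, which then agrees with the MANOVA allowance.

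Cost: a sentence or two of text, one changed count, and three of 126 error degrees of freedom. Age, sex and education are already needed to match the HA, so no new measurement is required.
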